DTSQc © [name] 11.9.96 English for Canada 20.1.06 (from Std UK English rev. 4.3.98; generic intro. rev. 28.2.02)
 Health Psychology Research, UK. www.healthpsychologyresearch.com

Diabetes Empowerment Scale – Short Form (DES-SF)

Follow-up time: Baseline, 6 weeks, 12 weeks

Date completed

In general, I believe that I:

1. know what part(s) of taking care of my diabetes that I am dissatisfied with. (DESSF1)
5 – Strongly Agree. 4 – Somewhat Agree. 3 – Neutral. 2 – Somewhat Disagree. 1 – Strongly Disagree.
2. am able to turn my diabetes goals into a workable plan. (DESSF2)
5 – Strongly Agree. 4 – Somewhat Agree. 3 – Neutral. 2 – Somewhat Disagree. 1 – Strongly Disagree.
3. can try out different ways of overcoming barriers to my diabetes goals. (DESSF3)
5 – Strongly Agree. 4 – Somewhat Agree. 3 – Neutral. 2 – Somewhat Disagree. 1 – Strongly Disagree.
4. can find ways to feel better about having diabetes. (DESSF4)
5 – Strongly Agree. 4 – Somewhat Agree. 3 – Neutral. 2 – Somewhat Disagree. 1 – Strongly Disagree.
5. know the positive ways I cope with diabetes related stress. (DESSF5)
5 – Strongly Agree. 4 – Somewhat Agree. 3 – Neutral. 2 – Somewhat Disagree. 1 – Strongly Disagree.
6. can ask for support for having and caring for my diabetes when I need it. (DESSF6)
5 – Strongly Agree. 4 – Somewhat Agree. 3 – Neutral. 2 – Somewhat Disagree. 1 – Strongly Disagree.
7. know what helps me stay motivated to care for my diabetes. (DESSF7)
5 – Strongly Agree. 4 – Somewhat Agree. 3 – Neutral. 2 – Somewhat Disagree. 1 – Strongly Disagree.
8. know enough about myself as a person to make diabetes care choices that are right for me. (DESSF8)
5 – Strongly Agree. 4 – Somewhat Agree. 3 – Neutral. 2 – Somewhat Disagree. 1 – Strongly Disagree.

Scoring

DES-SF score (average of the 8 items) (DESSFscore).

Problem Areas in Diabetes Questionnaire

Follow-up time: Baseline, 6 weeks, 12 weeks

Date completed

Items PAID01 – PAID20, scored 0-4 as below.

Problem Areas In Diabetes (PAID) Scale

Instructions: Which of the following diabetes issues are **currently** a problem for you? Tick the box that gives the best answer for you. Please provide an answer for each question.

	Not a problem	Minor problem	Moderate problem	Somewhat serious problem	Serious problem
1 Not having clear and concrete goals for your diabetes care?	 0	 1	 2	 3	 4

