14 Not accepting your diabetes?	 0	 1	 2	 3	 4
15 Feeling unsatisfied with your diabetes physician?	 0	 1	 2	 3	 4
16 Feeling that diabetes is taking up too much of your mental and physical energy every day?	 0	 1	 2	 3	 4
17 Feeling alone with your diabetes?	 0	 1	 2	 3	 4
18 Feeling that your friends and family are not supportive of your diabetes management efforts?	 0	 1	 2	 3	 4
19 Coping with complications of diabetes?	 0	 1	 2	 3	 4
20 Feeling burned out by the constant effort needed to manage diabetes?	 0	 1	 2	 3	 4

© Joslin Diabetes Center, 1999 (www.joslin.org). All rights reserved. The copyright holder/developer has given permission for the questionnaire to be reproduced in this guide. Readers of the guide are permitted to reproduce the questionnaire for clinical use and non-commercial research purposes. Readers of the guide are not permitted to use the questionnaire for commercial research purposes and must seek permission from the copyright holder/developer to do so.

Scoring

Sum of for each item PAID01-PAID02 multiplied by 1.25 (PAIDscore).

UK Diabetes and Diet Questionnaire (UKDDQ)

Follow-up time: Baseline, 6 weeks, 12 weeks

Date completed

Items UKDDQ01-25, scored A-F as below.

Name: _____

Date: _____

Think about your diet over the last MONTH. Circle the answer that best applies to you. Put the letter score in the ovals.

1. How often did you eat a portion of vegetables?

Include fresh, tinned and frozen vegetables and pulses like lentils and kidney beans.

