We are interested in finding out about the kinds of physical activities that people do as part of their everyday lives. The questions will ask you about the time you spent being physically active in the last 7 days. Please answer each question even if you do not consider yourself to be an active person. Please think about the activities you do at work, as part of your house and yard work, to get from place to place, and in your spare time for recreation, exercise or sport.

Think about all the vigorous activities that you did in the last 7 days. Vigorous physical activities refer to activities that take hard physical effort and make you breathe much harder than normal. Think only about those physical activities that you did for at least 10 minutes at a time.

1. During the **last 7 days**, on how many days did you do **vigorous** physical activities like heavy lifting, digging, aerobics, or fast bicycling?
 _____ days per week (IPAQ1days)
 No vigorous physical activities → Skip to question 3. (IPAQ1none; if checked, set IPAQ1days and IPAQ2mins to 0)
2. How much time did you usual spend doing **vigorous** physical activities on one of those days?
 _____ hours per day (no specific variable name – auto-fills IPAQ2mins)
 _____ minutes per day (IPAQ2mins)
 Don't know / Not sure (IPAQ2dk; if checked, set IPAQ2mins to -9)

Think about all the moderate activities that you did in the last 7 days. Moderate activities refer to activities that take moderate physical effort and make you breathe somewhat harder than normal. Think only about those physical activities that you did for at least 10 minutes at a time.

3. During the **last 7 days**, on how many days did you do **moderate** physical activities like carrying light loads, bicycling at a regular pace, or doubles tennis? Do not include walking.
 _____ days per week (IPAQ3days)
 No moderate activities → Skip to question 5. (IPAQ3none; if checked, set IPAQ3days and IPAQ4mins to 0)
4. How much time did you usual spend doing **moderate** physical activities on one of those days?
 _____ hours per day (no specific variable name – auto-fills IPAQ4mins)
 _____ minutes per day (IPAQ4mins)
 Don't know / Not sure (IPAQ4dk; if checked, set IPAQ4mins to -9)

Think about the time you spent walking in the last 7 days. This includes at work and at home, walking to travel from place to place, and any other walking that you have done solely for recreation, sport, exercise, or leisure.

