5. During the **last 7 days**, on how many days did you **walk** for at least 10 minutes at a time?
 _____ days per week (IPAQ5days)
 No walking → Skip to question 7. (IPAQ5none; if checked, set IPAQ5days and IPAQ6mins to 0)
6. How much time did you usually spend **walking** on one of those days?
 _____ hours per day (no specific variable name – auto-fills IPAQ6mins)
 _____ minutes per day (IPAQ6mins)
 Don't know / Not sure (IPAQ6dk; if checked, set IPAQ6min to -9)

The last question is about the time you spent **sitting** on weekdays during the **last 7 days**. Include time spent at work, at home, while doing course work and during leisure time. This may include time spent sitting at a desk, visiting friends, reading, or sitting or lying down to watch television.

7. During the **last 7 days**, how much time did you spend sitting on a week day?
 _____ hours per day (no specific variable name – auto-fills IPAQ7mins)
 _____ minutes per day (IPAQ7mins)
 Don't know / Not sure (IPAQ7dk; if checked, set IPAQ7mins to -9)

Summary scores

Treat responses of -9 as 0.

Walking MET-minutes / week (metmin_walk) = $3.3 * \text{IPAQ5days} * \text{IPAQ6mins}$

Moderate MET-minutes / week (metmin_mod) = $4.0 * \text{IPAQ3days} * \text{IPAQ4mins}$

Vigorous MET-minutes / week (metmin_vig) = $8.0 * \text{IPAQ1days} * \text{IPAQ2mins}$

Total MET-mins / week (metmin_tot) = metmin_walk + metmin_mod + metmin_vig.

Summary categories

IPAQhepa = 1 if ($\text{IPAQ1days} \geq 3$ & $\text{metmin_tot} \geq 1500$) or ($(\text{IPAQ5days} + \text{IPAQ3days} + \text{IPAQ1days}) \geq 7$ & $\text{metmin_tot} \geq 3000$); else IPAQhepa = 0.

IPAQminactive = 1 if ($\text{IPAQ1days} \geq 3$ & $\text{IPAQ2mins} \geq 20$) or ($\text{IPAQ3days} \geq 5$ & $\text{IPAQ4mins} \geq 30$) or ($(\text{IPAQ5days} + \text{IPAQ3days} + \text{IPAQ1days}) \geq 5$ & $\text{metmin_tot} \geq 600$); else IPAQminactive = 0.

IPAQinactive = 1 if IPAQhepa = 0 & IPAQminactive = 0; else IPAQinactive = 0.

Health-Related Quality of Life – EQ-5D-5L

Follow-up time: Baseline, 6 weeks, 12 weeks

Date completed

Sample worksheet shown below.

Items named MO, SC, UA, PD, AD, each taking a value between 1 and 5.

Under each heading, please tick the ONE box that best describes your health TODAY.

MOBILITY

I have no problems in walking about

Levels of perceived problems
are coded as follows

1
 2
 3 Level = 2
 4
 5

I have slight problems in walking about

I have moderate problems in walking about

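### Appendix 5.4 scores unknown activity minutes as no activity (IPAQ), and the distress score formula (PAID) has a misprinted item range; minor, secondary outcomes only

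*Combined protocol and SAP*

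**What the plan says.** **IPAQ (Appendix 5.4).** For vigorous, moderate and walking activity the form asks for days, then usual minutes on such a day. A respondent who cannot give the minutes ticks a don't-know box. For vigorous activity the instruction is "IPAQ2dk; if checked, set IPAQ2mins to -9"; the moderate item works the same way. For walking it reads "IPAQ6dk; if checked, set IPAQ6min to -9", although the score uses a variable spelled `IPAQ6mins`. The summary-score rule is then "Treat responses of -9 as 0".

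Absence of activity has its own box, for example "IPAQ5none; if checked, set IPAQ5days and IPAQ6mins to 0". The vigorous and moderate sections tell the respondent "Think only about those physical activities that you did for at least 10 minutes at a time", and the walking item asks for days of walking "for at least 10 minutes at a time".

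**PAID (Appendix 5.4).** The form states "Items PAID01 – PAID20, scored 0-4 as below", and Table 1 in Section 10 also gives 20 items. The scoring line reads "Sum of for each item PAID01-PAID02 multiplied by 1.25 (PAIDscore".

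**Use.** Section 10 makes change from baseline at 6 and 12 weeks on these instruments a secondary outcome. Section 14 analyses the scores as continuous by linear regression and calls secondary outcomes hypothesis-generating.

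**The concern.** The IPAQ rule gives a person who was active for an unknown time the same score as a person who was not active at all. By the form's own definition of an active day, that score is impossible when days are above 0. Because the outcome is a change score, a don't-know answer at one visit and a figure at the other is recorded as a large gain or loss of activity that did not happen.

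Physical activity is a named secondary objective (Section 4), and Section 17 presumes that any glycemic benefit comes through diet and lifestyle. The IPAQ is the instrument for the activity part of that explanation.

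Appendix 5.4 supplies variable names and formulas for the electronic forms, the lead statistician is still to be named, and the analysts are unblinded (Section 6). Scoring rules are therefore best settled in the text before data by arm are seen. The same applies to the PAID item range.

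**Working it through.** The plan states no figure on this point, so there is none to reproduce. The check applies the Appendix 5.4 formulas directly.

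**Inputs from the documents**
- MET weights per day-minute: walking 3.3, moderate 4.0, vigorous 8.0. The total is their sum.
- Minimum for a counted day: 10 minutes.
- `IPAQhepa` = 1 if vigorous days ≥ 3 and total ≥ 1500, or summed days ≥ 7 and total ≥ 3000.
- `IPAQminactive` = 1 if vigorous days ≥ 3 at ≥ 20 min, or moderate days ≥ 5 at ≥ 30 min, or summed days ≥ 5 and total ≥ 600.
- `IPAQinactive` = 1 if both of the others are 0.
- PAID: 20 items, each 0 to 4, multiplier 1.25.
- 80 completers, 40 per arm (Section 14).

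**Assumed, because the documents give no values:** don't-know rates of 5%, 10% and 20%, and the minutes in the examples.

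**1. Lowest possible score with 7 active days (MET-min/week)**
- Moderate: 4.0 × 7 × 10 = 280
- Vigorous: 8.0 × 7 × 10 = 560
- Walking: 3.3 × 7 × 10 = 231

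The rule gives 0 in each case. The walking line needs `IPAQ6min` read as `IPAQ6mins`. Coded literally, the -9 never reaches the walking formula, and walking would be left blank instead of zero.

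**2. False change in one person.** With the name corrected, take 7 walking days at an assumed 30 min at both visits: 3.3 × 7 × 30 = 693 each time, true change 0. A don't-know answer at baseline only gives 693 − 0 = +693. At follow-up only, it gives −693.

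Let r be the chance that any domain is unknown at a visit. The share with a don't-know at exactly one of two visits is 0 if answers are fully concordant. If they are independent it is 2r(1 − r) = 9.5%, 18% and 32% at r = 5%, 10% and 20%.

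**3. Effect on the comparison of arms.** Let q be the follow-up don't-know rate among those active in a domain, unrelated to how active they are, and let μ1 and μ0 be the true arm means.
- Equal q: (1 − q)μ1 − (1 − q)μ0 = (1 − q)(μ1 − μ0). A true difference keeps 95%, 90% or 80% of its size at q = 5%, 10% or 20%, and noise is added.
- Unequal q1 and q0 with no true difference (both means μ): the spurious difference is (q0 − q1)μ. With an assumed μ = 693 and rates of 10% and 20%, that is 0.10 × 693 = 69.3 MET-min/week.
- Rates that differ between visits shift the mean change within each arm.

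**4. Categories.** Assume 3 vigorous days at 60 min and 5 walking days at 30 min.
- Minutes known: 8.0 × 3 × 60 + 3.3 × 5 × 30 = 1440 + 495 = 1935, so `IPAQhepa` = 1.
- Vigorous minutes unknown: 0 + 495 = 495. Every condition fails, so `IPAQinactive` = 1.
- With the 10-minute minimum in place of zero: 8.0 × 3 × 10 + 495 = 735, with 8 summed days. That meets the ≥ 600 condition, so the form's own content rules out the inactive label.

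**5. PAID.** 20 × 4 × 1.25 = 100. The printed range gives 2 × 4 × 1.25 = 10.

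**The case against.** The zero rule is explicit, set in advance and identical in both arms. Days and don't-know flags are stored, so nothing is irrecoverable. The outcomes are hypothesis-generating, and no don't-know frequency is given, so no calculation can show that the effect is material. Setting scores to missing discards data in a plan that names no missing-data method. All of this stands. It limits the point to minor, but it does not make a score of 0 possible for someone who reports active days.

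It might be argued that equal rates in the two arms add only noise. That is true when the arms do not differ. When they do, the difference is also diluted, as step 3 shows.

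For PAID, the objection is that nobody would score two items. That is accepted. The form and Table 1 both give 20 items, the multiplier yields a 0-100 scale only with 20, and no two-item score is mentioned anywhere. A reader might infer that distress will be reported on a 0-10 scale, but the documents do not support that.

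A reader might also suspect the diet score (UKDDQ), because item 22 is missing from the list of omitted items and items 19, 21 and 23 allow an answer with no score. The documents do not show a fault there. Item 22 has no letters and so adds nothing, the plan nowhere says that an unscored answer counts as 0, and the form's scoring page is not in the available text.

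**Conclusion.** The IPAQ rule is wrong as written: it assigns a value that the form itself excludes whenever days are above 0 and minutes are unknown. Per person and domain, the understatement over 7 days is at least 280 (moderate), 560 (vigorous) or 231 MET-min/week (walking, with the variable name corrected). It can also move a person from the highest activity category to the lowest.

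The effect on the trial's physical activity result is unknown. It depends on how often people answer don't know, how consistently they do so across visits, and whether rates differ by arm; the documents give none of these. It would go too far to infer that the activity comparison is materially biased, or that the primary result is touched: HbA1c and the sample size do not use these scores.

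The PAID line is a misprint in a formula, with consequences only if it is programmed literally. Overall the point is minor, and certain as to the text.

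**What to change.** **IPAQ, in Appendix 5.4 and the calculated fields:**
- When days are above 0 and minutes are -9, set that domain and `metmin_tot` to missing. Keep the other domain scores.
- Set `IPAQhepa`, `IPAQminactive` and `IPAQinactive` to missing unless the known items already determine the category. Otherwise the else-zero wording sets the first two to 0 and labels a person with a missing total inactive. State whether the 10-minute minimum counts as known.
- Report don't-know counts by arm and visit.
- Keep the zero rule as a sensitivity analysis.
- Correct `IPAQ6min` to `IPAQ6mins`.

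**PAID:** correct PAID01-PAID02 to PAID01-PAID20.

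**Cost.** These are edits to a few lines and use data already collected. The real price is lost IPAQ change totals. For a two-visit contrast among 80 completers, with r = 5%, 10% and 20% per visit:
- fully concordant answers: 80r = 4, 8 and 16 lost;
- independent answers: 80 × (1 − (1 − r)²) = 7.8, 15.2 and 28.8, about 8, 15 and 29 lost.

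An analysis that needs all three visits would lose 80 × (1 − (1 − r)³), about 11, 22 and 39, under independence. Since Section 14 names no missing-data method, the counts and the zero-rule analysis should appear beside the main result.

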Appendix 5.5: HbA1c and Time in Range Form

HbA1c Report Form

Research assistant to complete

Patient study ID

Follow-up time: Baseline, 12 weeks

HbA1c value

Date of HbA1c

isCGM Time-in-Range Report Form

Research assistant to complete

Patient study ID

Follow-up time: 12 weeks

For adults randomized to the isCGM group only

Date of first sensor start:

Date of second sensor start:

Date of third sensor start:

Referring to the first two weeks of isCGM sensor use:

- Start date:
- Time-in-range (3.9-10.0 mmol/L) (%):
- Time-above-range (>10.0 mmol/L and <= 13.9 mmol/L):
- Time-above-range – severe (> 13.9 mmol/L):
- Time-below range (sum of < 3.9 mmol/L and < 3.0 mmol/L):
- Glucose Management Indicator (GMI) (%):
- Coefficient of variation (CV):

Referring to the last two weeks of isCGM sensor use:

- Start date:
- Time-in-range (3.9-10.0 mmol/L) (%):
- Time-above-range (>10.0 mmol/L and <= 13.9 mmol/L):
- Time-above-range – severe (> 13.9 mmol/L):
- Time-below range (sum of < 3.9 mmol/L and < 3.0 mmol/L):
- Glucose Management Indicator (GMI) (%):
- Coefficient of variation (CV):

Appendix 5.6: Adverse events report form

Patient study ID

Adverse event

- Diagnosis, if available
- Patient-report

Start date

Setting: Managed in the community, required EMS, required ED, required hospital admission.

Event details:

- Enclose ED chart or discharge summary if ED or hospital admission required
- Patient description of event

Investigator Review:

- Relationship to study treatment (definitely, possibly, not related)
- Outcome (resolved, persistent, death)
- Expected (yes, no)
- Serious (yes, no)

Definitions for adverse events form.

An Adverse Event (AE) is defined as any untoward medical occurrence, including an exacerbation of a pre-existing condition, in a patient in a clinical investigation who received a pharmaceutical product. The event does not necessarily have to have a causal relationship with this treatment.

A Serious Adverse Event (SAE) is defined as any AE which results in death, is immediately life-threatening, results in persistent or significant disability / incapacity, requires or prolongs patient hospitalization, is a congenital anomaly / birth defect, or is to be deemed serious for any other reason representing a significant hazard, which is comparable to the aforementioned criteria.

Relationship to study treatment will be determined in the medical judgement of a study investigator.

Appendix 6: Qualitative Sub-Study Interview Guides

iCUDE Trial Qualitative Sub-Study

Interview Guide

Interview Guide (Group 1: Trial Patients Randomized to Intervention)

I would like to start by thanking you for participating in this interview. I am interested in your perspectives regarding the FreeStyle Libre 2 continuous glucose monitor and your visits with the diabetes educator. Before we start our interview, I would like to ask you not to use names of people or institutions that may identify them. We will also remove all identifying information from the transcripts.

1. Did you have any thoughts or expectations about what using the FreeStyle Libre 2 would be like before you started it?
2. Can you tell me about your experience using the Libre 2 for the first time?
Probes: Was it easy or difficult to start using? What do you think about being able see your blood sugar on your cell phone? What did you think of your blood sugars the first day you measured them? How did they make you feel? Did you know what to make of them, or what to do about them?
3. What changes did the Libre 2 lead to in terms of what you eat or what you do during the day? How difficult was it to make those changes?
Probes: Can you think of anything that helped you make those changes? Anything that might have made it harder to make those changes?
4. Has the Libre 2 changed how you think or feel about your diabetes?
5. What kind of support or resources did you have to help with your diabetes before this trial?
6. Can you tell me about the kind of impact meeting with the diabetes educator had on you?
Probes: How long was the encounter? How did it feel talking to the diabetes educator? What did you learn during the encounter? Did you make a plan? What did you like best about the encounter? What would you like to be different?
7. Can you tell me about the kind of impact meeting with the diabetes educator had on your ability to use the Libre 2? To look after your diabetes?
Probes: How about in terms of changes to your diet and activity?
8. Was the second educator encounter different from the first?
Probes: Were there things you learnt that were different in the second encounter, from the first? What would the perfect number of encounters be? How far apart should they be?
9. Is the FreeStyle Libre 2 something you'd consider using again in the future? Why or why not?
10. Do you have goals for your diabetes moving forward?
Probes: Can you describe your goals? What do you think about these goals? How optimistic are you that you will be able to follow through with your goals?

Version (1): March 24, 2022

1

11. Is there anything else you would like to share about using the Libre 2 or meeting the diabetes educator?

Thank you very much for speaking with me. We would be pleased to offer you a small amount of money (\$20) in appreciation for your time. You can expect it in the mail – please let us know if you don't receive it.

Interview Guide (Group 2: Trial Patient Randomized to Enhanced Usual Care)

I would like to start by thanking you for participating in this interview. I am interested in your perspectives about looking after your diabetes and your visits with the diabetes educator. Before we start our interview, I would like to ask you not to use names of people or institutions that may identify them. We will also remove all identifying information from the transcripts.

1. Do you know how well your diabetes was looked after before you met the educator? How did you feel about your diabetes before you met the educator?
Probes: Were you doing anything in particular to make your diabetes better, or to keep it from getting worse? What kind of support or resources did you have to help with your diabetes?
2. Can you tell me about the kind of impact meeting with the diabetes educator had on you?
Probes: How long was the encounter? How did it feel talking to the diabetes educator? What did you learn during the encounter? Did you make a plan? What did you like best about the encounter? What would you like to be different?
3. Was the second educator encounter different from the first?
Probes: Were there things you learnt that were different in the second encounter, from the first? What would the perfect number of encounters be? How far apart should they be?
4. Did you start measuring your blood sugars at any time during the trial? Do you feel that measuring your blood sugars could have been useful?
5. Do you have goals for your diabetes moving forward?
Probes: Can you describe your goals? What do you think about these goals? How optimistic are you that you will be able to follow through with your goals?
6. Is there anything else you would like to share about meeting the diabetes educator?

Thank you very much for speaking with me. We would be pleased to offer you a small amount of money (\$20) in appreciation for your time. You can expect it in the mail – please let us know if you don't receive it.

Interview Guide (Group 3: Providers)

I would like to start by thanking you for participating in this interview. I am interested in your perspectives regarding looking after adults with early diabetes – those who are not on insulin, but who need additional blood sugar lowering to get to target. Specifically, I want to talk about using the FreeStyle Libre 2 continuous glucose monitor with these patients. Before we start our interview, I would like to ask you not to use names of people or institutions that may identify them. We will also remove all identifying information from the transcripts.

1. What is your previous experience looking after patients using the Libre or Libre 2 CGM?
2. What difference did the Libre 2 make for our trial patients who were not on insulin?
Would you consider the Libre 2 useful or not useful, in this population? Why or why not?
Probe: (If not useful, then what would the Libre 2 being useful look like?)
3. Are there patient factors that determine whether the Libre 2 is useful for an individual or not? What are they?
Probe: Are they related to knowledge? Skill? Motivation? Supports? Environment? Diet? Activity? Are there other factors you'd like to mention?
4. Can you tell me about your encounters with patients using the CGM?
Probes: How long was the encounter? How did it feel from your perspective? Is there anything you'd like to highlight as working particularly well? Anything you would think about doing differently during these encounters?
5. Were you able to relate the Libre 2 results to things going on in the patients' lives? Were you able to build plans of action with your patients using Libre 2 results?
Probe: How challenging did you find this? What kind of plans did you typically leave with? Did patients need a lot of convincing to take these steps?
6. Do you feel you have the right training or resources to help patients at this stage of their diabetes, to use the CGM and improve their diabetes?
7. Is there anything else you would like to share about help adults with diabetes who are not on insulin use the Libre 2?

Thank you very much for speaking with me. We would be pleased to offer you a small amount of money (\$20) in appreciation for your time. You can expect it in the mail – please let us know if you don't receive it.

